6.4.1 Adverse Events

AEs are displayed in tables and listings by SOC and PT, unless specified otherwise.

Refer to the Core SAP for AE start date imputation, AE counting rules and frequency table specifications, definition of related to study drug, definition of treatment-emergent adverse events (TEAEs), definition of AEs of special interest, reporting of deaths, and AE listing contents. Exposure-adjusted multiple occurrences of unique AEs (Section 6.4.1.5 of the Core SAP) does not apply.

For purposes of applying Section 6.4.1.2 of the Core SAP (definition of TEAE), an AE with non-missing start time is considered pre-treatment if the start date/time of the AE is prior to treatment start date/time. Furthermore, the “first occurrence” of an AE means the earliest imputed start date or earliest start date/time, where an AE with non-missing start date/time is deemed prior to an AE with missing start time and an imputed start date on the same date.

A by-subject AE listing is provided for the enrolled analysis set. Notwithstanding Section 6.4.1.7 of the Core SAP, “treatment of event” is not listed.

6.4.1.1 Deaths

Deaths are identified from any the following sources:

- AE CRF with any of the following: PT of “death”; reported term containing “death”; outcome of fatal; “yes” response to any death-related question (e.g., “Did the AE result in death?”; “Is a death certificate available?”; “Is an autopsy report available?”); complete or partially complete death date (see Section 7.1)
- Disposition CRF: subject status of “Death.”

The by-subject listing of deaths is provided for the enrolled analysis set, and displays all CRF sources of death, safety analysis period, death date (see Section 7.1), study day derived from the death date, treatment day derived from the death date, and the following AE parameters: non-imputed start date and end date; SOC; PT; verbatim term; outcome; and response to the question “Fatal”.

6.4.1.2 AE Overview

An AE overview without SOC and PT presents the number and percentage of subjects with any of the following AEs: any AE; mild AE; moderate AE; severe AE; moderate or severe AE; AE related to study drug; SAE; SAE related to study drug; AE leading to study drug discontinuation; hepatic-related AE; cardiovascular AE; and suicidality AE.

An AE overview is produced for each analysis period (pre-treatment, on-treatment) for the treated analysis set.

6.4.1.3 On-treatment AEs by SOC and PT

On-treatment AEs are tabulated by SOC and PT for the treated analysis set for the following endpoints:

- AEs by intensity
- AEs associated with study drug by intensity
- AEs by relationship to study drug (related, not related, not reported)
- SAEs
- AEs leading to study drug discontinuation
- Hepatic-related AEs by intensity *
- Cardiovascular AEs *
- Suicidality AEs *.

AEs of special interest are asterisked (“*”). AEs are displayed in descending order of rimegepant frequency within SOC and PT.

6.4.2 Laboratory Tests

Laboratory tests are analyzed using results from a central laboratory and are collected at the following visits: Screening, EOT and Unscheduled. Laboratory tests are slotted into safety analysis periods (pre-treatment and on-treatment) according to the laboratory collection date and time, as available. Some tabulations are provided for the on-treatment period only, as specified below.

Fasting time is not collected; therefore, cholesterol and triglycerides are analyzed as separate laboratory test parameters according to fasting status (last 8 hours): fasting; non-fasting; overall (see Section 6.4.2 of the Core SAP).

Clinically significant laboratory abnormalities are identified as grade 3 to 4 laboratory test results. Refer to Section 6.4.2.1 of the Core SAP for laboratory tests of clinical interest for analyses, including identification of those with toxicity grades. If a toxicity grade depends on age, then age is defined as age recorded on the CRF.

Estimated glomerular filtration rate (eGFR) is derived using the modification of diet in renal disease (MDRD) formula. Notwithstanding Section 2.2 of the Core SAP, eGFR is not separately derived but is provided as reported by the central laboratory.

Laboratory test groups of clinical interest includes hematology, serum chemistry, and urinalysis.

TLFs show data in the Systeme International (SI) unit system, if applicable. Tables present results by treatment group and overall, and laboratory tests alphabetically within laboratory test group, as applicable.

6.4.2.1 *Laboratory Test Abnormalities*

Laboratory test abnormalities are tabulated as the number and percentage of subjects in the treated analysis set in the frequency tables specified in Section 6.4.2.2 of the Core SAP. This is provided for the on-treatment period only.

6.4.2.2 *Liver Function Test Elevations*

Liver function test (LFT) elevations are tabulated for laboratory tests as specified in Section 6.4.2.3 of the Core SAP (as applicable to single-dose studies).

LFT Elevations: Cumulative, Mutually Exclusive, and Composite

The number and percentage of subjects with LFT elevations are tabulated separately for each analysis period (pre-treatment, on-treatment) for the treated analysis set. LFT elevations are based on fold changes above ULN.

LFT ULN Shifts from Baseline to Worst Elevation

LFT ULN shifts from baseline to the worst (highest) on-treatment LFT elevation are tabulated as the number and percentage of subjects in the treated analysis set in pre-specified elevation categories.

6.4.2.3 *LFT Plots*

An evaluation of drug-induced serious hepatotoxicity (eDISH) scatter plot is produced, as specified in Section 6.4.2.4 of the Core SAP, separately for each analysis period (pre-treatment, on-treatment). By-subject longitudinal LFT plots are not produced.

6.4.2.4 *Laboratory Test Changes from Baseline Table*

Values and changes from baseline in laboratory tests are tabulated descriptively as continuous variables over time at baseline and EOT.

The table displays results by laboratory tests alphabetically within laboratory test group.

Multiple values in analysis visit windows are handled as set forth in Section 7.3.

6.4.2.5 *Laboratory Test Listings*

By-subject Listings of Laboratory Test Results

All laboratory test listings will be based on the enrolled analysis set.

A by-subject listing of the following select laboratory tests is provided for subjects with at least one laboratory assessment of grade 3 or 4 abnormality or a positive pregnancy test result: hematology results, serum chemistry results, and urinalysis results. If there is a positive pregnancy test, defined as a serum or urine pregnancy test with either (1) “positive” character value, or (2) numeric value ≥ 25 U/L, the listing will also include all pregnancy test results over time.

Refer to Section 6.4.2.6 of the Core SAP for listing contents as applicable to this study.

By-subject Listing of LFT Values and Ratios to ULN

Liver function test (LFT) values and ratios to upper limit of normal (ULN) (i.e., alanine aminotransferase [ALT], aspartate aminotransferase [AST], total bilirubin [TBL] and alkaline phosphatase [ALP]) are displayed for SI units. The listing displays all LFT results over time for subjects with select LFT elevations (ALT or AST $> 3x$ ULN; ALP or TBL $> 2x$ ULN) at any time point. Refer to Section 6.4.2.6 of the Core SAP for listing contents as applicable to this study.

6.4.3 *Vital Signs and Physical Measurements*

Vital signs include systolic blood pressure, diastolic blood pressure, heart rate, and temperature. These parameters are measured at Screening, Baseline, and EOT. Vital signs are slotted into safety analysis periods (pre-treatment, on-treatment) according to the measurement date. Vital signs are tabulated for the on-treatment analysis period (see Section 7.2) for the treated analysis set.

Physical measurements include height, weight, and body mass index (where height and weight are measured at Screening only). Physical measurements are slotted into safety analysis periods (pre-treatment, on-treatment) according to the measurement date.

6.4.3.1 *Vital Sign Changes from Baseline*

Values and changes from baseline in vital signs are tabulated descriptively as continuous variables at baseline and EOT. Physical measurements (i.e. weight, height, and BMI) are not included in this display.

Multiple values in analysis visit windows are handled as set forth in Section 7.3.

6.4.3.2 *Vital Signs Abnormalities*

Vital sign abnormalities are tabulated as the number and percentage of subjects in the treated analysis set meeting categories specified in Section 6.4.3.2 of the Core SAP during the on-

treatment analysis period, except weight change from baseline is not calculated. Analyses are based on the subset of subjects with non-missing data in the on-treatment analysis period for a given parameter.

6.4.3.3 Vital Signs and Physical Measurements Listing

Refer to Section 6.4.3.3 of the Core SAP for details on the by-subject vital signs and physical measurement listing, as applicable to this study. All vital signs and physical measurements listings will be based on the enrolled analysis set.

6.4.4 Procedures

Procedures are listed for the enrolled analysis set using the Concomitant Procedures CRF. The listing includes the name of the procedure/surgery, SOC and PT, the date of the procedure/surgery, and analysis periods. See Section 6.4.5 of the Core SAP for further details. Procedures are slotted into safety analysis periods according to the procedure date. Note that procedures are slotted like AEs, but without date imputation (see Section 7.2).

6.4.5 Suicidality

The C-SSRS is a clinician administered questionnaire used for suicide assessment. The C-SSRS Screening version is used at the Screening Visit and the Since Last Visit version is used at subsequent visits. C-SSRS is measured at Screening, Baseline and EOT. The C-SSRS Assessment is intended to help establish a person's immediate risk of suicide.

At the Screening Visit, the recall period for completing the C-SSRS is past 12 months for ideation, and 10 years for attempt and behavior; at all other visits, the recall period for completing the C-SSRS is since the last visit.

Refer to the Core SAP for the definitions of C-SSRS parameters and specifications for tabulation. However, notwithstanding Section 6.4.6.2 of the Core SAP, C-SSRS results are not separately tabulated by analysis periods but instead tabulated by visit (Screening, Baseline, and EOT). Unscheduled or early termination visits following treatment are reassigned as specified in Section 7.3; unscheduled or early termination visits prior to treatment are not reassigned or tabulated.

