The number and percentage of subjects that use rescue medication within 24 hours post-dose are analyzed. Subjects who used rescue medication as of 24 hours post-dose are deemed failures, and subjects who did not use rescue medication as of 24 hours are deemed successes. For clarity, failure is the event being modeled (i.e. rescue medication use within 24 hours) in this analysis.

Refer to Section 6.2.6.3 for the definition of rescue medication. A rescue medication would be deemed used as of 24 hours post-dose if the date/time of first rescue medication use is strictly } 24 hours after the date/time of dosing, notwithstanding Section 6.3.1 of the SAP. Subjects with a rescue medication start date on or before study drug start date/time + 24 hours and missing rescue medication start time are excluded. Subjects who report non-study medication on the Rescue Medication CRF with a missing rescue medication date, or a partial medication date that is consistent with being used within 24 hours of dosing, are also excluded. Regardless of the foregoing, if a subject has at least one rescue medication use with non-missing start time that is } 24 hours after the date/time of dosing, the subject will be included in the analyses and deemed a failure.

No analysis window around the 24-hour post-dose time point is used.

The analysis follows the same methodology set forth in Section 6.3.3.3. A forest plot is produced depicting the risk difference for rescue medication use within 24 hours post dose. The risk difference for each strata will be presented, as well as the overall common risk difference.

Time to rescue medication use through 24 hours post-dose is assessed by treatment group as follows:

- Kaplan-Meier plot and table using 2-hour time intervals (i.e., 0 to 2, > 2 to 4, ... , > 24). The Kaplan-Meier plot displays the percentage of subjects taking rescue medication

data without imputation and regardless of rescue medication use. In these tables of safety parameters, if a subject has multiple values in the end of treatment analysis visit window (see Section 7.3), then the last non-missing value measured in the analysis period is used. See Sections 6.3.4.1, 6.4.4.1, and 6.4.2.4 for further handling of ties on the same measurement date or time.

By-subject listings of safety parameters are described in subsections and identify on-treatment data.

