6.4.6 Safety Narrative Subject Identifiers Listing

A by-subject listing of safety narrative subject identifiers is provided for the following select events and analysis sets as columns:

- All deaths on-treatment or during follow-up, regardless of treatment
 - SAEs on-treatment or during follow-up for rimegepant-treated subjects, regardless of relationship to study drug
-

- Any AE leading to discontinuation of study drug for rimegepant-treated subjects, regardless of relationship to study drug
- On-treatment events of special interest for rimegepant-treated subjects:
 - ALT or AST > 3x ULN
 - ALT or AST > 3x ULN concurrent with TBL > 2x ULN
 - TBL or ALP > 2x ULN
 - Select hepatic-related AE, i.e., PT containing cirrhosis, hepatic failure, hepatitis, jaundice, or liver failure
 - Cardiovascular AE
 - Suicidality AE

Refer to the Core SAP for additional details. The listing flags subjects with select events.

Should the criteria stated in the Biohaven Rimegepant Safety Narrative Scope conflict with the criteria above, the Biohaven Rimegepant Safety Narrative Scope will take precedence.

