7.3 Analysis Visit Windows

Refer to Protocol Section 4.2 for the schedule of assessments.

Study days are calculated from the randomization date as follows:

- Measurement date – randomization date + 1, if measurement date > randomization date
- Measurement date – randomization date, if measurement date < randomization date.

Treatment days are calculated from the study drug dose date as follows:

- Measurement date – study drug dose date + 1, if measurement date > study drug dose date
- Measurement date – study drug dose date, if measurement date < study drug dose date.

Analysis visit windows for safety parameters are presented in Table 4.

Table 4: Analysis Visit Windows for Safety Parameters

Analysis Visit	Analysis-Specified Interval
Screening	
 • } Study day – 1 or both study day and treatment day missing • } Treatment day – 1 *
Baseline	Study day 1
End of treatment	
 • ;; Study day 2 • ;; Treatment day *

*Applies only to subjects who took study drug but were not randomized

Notwithstanding Sections 6.4.3.1 of the Core SAP, multiple values in analysis visit windows are handled as follows:

- The scheduled visit takes priority over unscheduled or early termination visits.
- If a subject does not have a scheduled visit, the unscheduled or early termination visit closest to the target date takes priority.

- If there are still multiple values on the same measurement date, then the last value collected timewise takes priority (if time is collected); if ties remain, the value with the highest ECG reference identifier, vital signs identifier, or laboratory barcode is used, as applicable.

For clarity, displays that tabulate baseline values tabulate the baseline value as defined in Section 7.5, rather than the value that maps to the Baseline Visit, unless otherwise explicitly noted (see Section 6.4.6).

For efficacy assessments collected on the eDiary, windows are imposed by the eDiary, as shown in Table 5. No additional analysis windows are imposed. The anchor point for the windows is the date/time of exposure, as defined in Section 7.1.

Table 5: Evaluation Intervals for Efficacy Analyses

Post-dose Evaluation	Analysis-Specified Interval	Target Time
15 min diary	10-20 min	Study medication start time + 15 min
30 min diary	25-35 min	Study medication start time + 30 min
45 min diary	40-50 min	Study medication start time + 45 min
60 min diary	55-65 min	Study medication start time + 60 min

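### The SAP's one-form-per-visit rule for the C-SSRS can leave a positive unscheduled post-dose form out of the C-SSRS table when the scheduled End of Treatment form is negative

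*SAP*

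**What the plan says.** **Tabulation.** SAP 6.4.5 departs from the Core SAP on one feature: "C-SSRS results are not separately tabulated by analysis periods but instead tabulated by visit (Screening, Baseline, and EOT"). EOT is the only one of these visits that follows dosing.

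**Extra forms after dosing.** The same section adds: "Unscheduled or early termination visits following treatment are reassigned as specified in Section 7.3". In SAP 7.3, Table 4 places such visits in the End of treatment window. The rules for several values in a window then state: "The scheduled visit takes priority over unscheduled or early termination visits". If there is no scheduled visit, "If a subject does not have a scheduled visit, the unscheduled or early termination visit closest to the target date takes priority".

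**General safety rule.** The introduction to SAP 6.4, just before 6.4.1, has a different rule for several values in the EOT window: "then the last non-missing value measured in the analysis period is used". It also yields one value per subject.

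**Recall period.** After Screening, "at all other visits, the recall period for completing the C-SSRS is since the last visit" (SAP 6.4.5). Protocol Table 1 and Protocol 6.3.5 agree.

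**Material held elsewhere.** SAP 6.4.5 also says: "Refer to the Core SAP for the definitions of C-SSRS parameters and specifications for tabulation". The Core SAP is incorporated by reference and is not among the public documents.

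**The concern.** Choosing one value per window is reasonable for repeated readings of the same quantity, such as blood pressure or a laboratory test. The Since Last Visit form is different. Each one reports on its own interval, and successive intervals do not overlap. Suppose ideation is recorded at an unscheduled post-dose visit. The scheduled EOT form then asks only about the days after that visit and can truthfully be negative. If the table shows only the EOT form, the interval containing the event is not represented.

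The C-SSRS is a listed safety measure (Protocol 3.3), and SAP version 2.0 kept it when outputs were cut. The table exists to show uncommon positive answers, so its derivation should not be able to omit one that was collected.

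**Working it through.** The plan states no figure on this point, so there is none to reproduce. The check applies the written rules to hypothetical sets of post-dose forms.

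**Inputs**
- Only post-dose column: EOT (SAP 6.4.5).
- Rule A: the scheduled form wins; with no scheduled form, the one nearest the target date is used (SAP 7.3). The target date is taken as day 7 after dosing. This is an assumption based on the EOT visit being within 7 (+2) days.
- Rule B: the last non-missing value in the window (SAP 6.4 introduction).
- Rule C: positive if any post-dose form is positive (the proposed rule).

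**Result shown in the EOT column** (1 = positive, 0 = negative; days counted from dosing)

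| Forms collected after dosing | Rule A | Rule B | Rule C |
|---|---|---|---|
| Unscheduled positive day 3; scheduled EOT negative day 7 | 0 | 0 | 1 |
| Unscheduled negative day 3; scheduled EOT positive day 7 | 1 | 1 | 1 |
| Scheduled EOT negative day 7; unscheduled positive day 12 | 0 | 1 | 1 |
| Scheduled EOT positive day 7; unscheduled negative day 12 | 1 | 0 | 1 |
| Unscheduled positive day 3; unscheduled negative day 6; no EOT form | 0 | 0 | 1 |
| Unscheduled positive day 3 only | 1 | 1 | 1 |

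The first row is the case at issue. The day-7 form covers days 3 to 7, and the interval up to day 3 is reported only on the form that was set aside. Rules A and B both lose it, so reconciling SAP 6.4 with 7.3 would not cure the problem. The rows are illustrations, not frequencies.

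**Can an EOT form follow a positive unscheduled form?** Yes. Protocol 6.5 asks subjects who discontinue to complete the EOT procedures, apart from those who withdraw consent for all procedures or can no longer consent freely.

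**How far back does the first post-dose form look?** Dosing may come up to 45 days after the Baseline Visit. With no visit in between, a form on day 3 after dosing can cover up to 45 + 3 = 48 days, of which 45 precede dosing. A scheduled EOT form on day 7 with no earlier post-dose form can cover up to 45 + 7 = 52 days. The pre-dose look-back therefore already exists under the current rule, but it limits what a positive form proves.

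**Size.** Each occurrence removes one subject from the table. At the planned 80 treated per arm, one subject is 1/80 = 1.25 percentage points. This shows scale only and does not estimate how often the case arises.

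**The case against.** **The Core SAP may already deal with this.** SAP 6.4.5 refers to it for C-SSRS parameters and tabulation, and SAP Section 1 gives it primacy where it is directly referenced or where this SAP is silent. It could contain an any-positive summary or a by-subject listing. This stands as a limit on certainty. However, 6.4.5 switches off tabulation by analysis period and sets its own handling of extra visits, so on that handling this SAP is not silent.

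**Reassignment may mean window mapping only.** The laboratory and vital-sign sections (SAP 6.4.2.4 and 6.4.3.1) expressly send multiple values to 7.3, and 6.4.5 does not. The final tie-break in 7.3 names only ECG, vital-sign and laboratory identifiers. This reading is possible but strained: mapping puts two forms in one EOT window, and 7.3 is where the plan says how that is resolved.

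**Last visit could mean last scheduled visit.** The EOT form would then cover the earlier interval. The documents do not say so.

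**Adverse events are a second route.** This largely stands. Protocol 6.3.5 requires immediate evaluation of any positive answer, and AE or SAE recording when the investigator determines risk. Suicidality AEs appear in the AE overview (SAP 6.4.1.2) and by SOC and PT (SAP 6.4.1.3), and all AEs are listed for enrolled subjects (SAP 6.4.1). What may remain uncovered is a positive answer not judged to indicate risk and not otherwise recorded as an AE.

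**Stronger readings that the documents do not support.** A reader might infer that post-dose suicidality disappears from the trial's reporting; the AE route and the unseen Core SAP rule out that conclusion. A reader might also infer that the form nearest to dosing is always the one dropped; in the third row of the table it is the later form. Nor is every positive post-dose form evidence of ideation after dosing, given the look-back. Finally, the narrative listing in SAP 6.4.6 is triggered by a "Suicidality AE" rather than by a C-SSRS answer, but that section defers to a separate narrative scope document that is not available, so a gap there is not established.

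**Conclusion.** The point holds as a limited defect in one table. Under either written selection rule, a positive unscheduled post-dose form followed by a negative scheduled EOT form does not appear in the C-SSRS tabulation.

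This rests on three assumptions: that the multiple-value rules in 7.3 (or the last-value rule in 6.4) apply to the C-SSRS, that the last visit includes unscheduled visits, and that the Core SAP adds no output showing the form.

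The case should be rare. The C-SSRS is scheduled only at Screening, Baseline and EOT, each subject takes one dose, and the study stopped early for low enrolment. It needs a modest correction and gives no reason to doubt the wider safety reporting.

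**What to change.** In SAP 6.4.5, replace the reliance on 7.3 for post-dose forms with wording such as:

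*The single-value selection in Section 7.3 does not apply to the C-SSRS. For the EOT column, the most severe ideation category and any suicidal behaviour across all post-dose forms (scheduled, unscheduled and early termination) are tabulated.*

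Add a table footnote that the first post-dose form's recall starts at the previous visit and may include time before dosing.

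The cost is two or three SAP sentences and a maximum-over-records derivation, with no new data. The small downside is that some pre-dose ideation may be counted in the post-dose column, which the footnote discloses. If the Core SAP already specifies such a summary, a cross-reference to it that states its precedence over 7.3 would be enough.

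A worst-case rule for pre-dose unscheduled forms and a C-SSRS trigger in the narrative listing are optional and not needed to resolve this point.
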